Sample Size: One of the stated goals of this study is to examine sex-specific lipolytic responses to CPAP withdrawal. We base our sample size on the ability to detect a difference in FFA elevation between men and women. In the 20 non-diabetics of our preliminary data, the average Δ FFA during CPAP withdrawal was 0.047 ± 0.04 mmol/l in men (n=13), and 0.021 ± 0.04 mmol/l in women (n=7). This yields a medium effect size (Cohen's $d = 0.65$). To detect a sex difference at 80% power at a significance level of 0.05, requires a sample size of 78 (39 men and 39 women). We anticipate potential technical problems (e.g. IV failures, hemolysis, and poor sleep efficiency) leading to loss of 15% data. Therefore, our target enrollment will be 92 subjects.

Early stopping rule

At any point in the study, the subject may decline to participate. Indications for stopping are the development of severe adverse events. The DSMB and IRB will be informed of any adverse events. Any serious adverse events will result in study discontinuation.

7. Risks

- a. Medical risks, listing all procedures, their major and minor risks and expected frequency.

Venipuncture: May be associated with discomfort and bruising. Infection or irritation (phlebitis) can occur at the IV site.

Phlebotomy: In total, the blood collected will be approximately 174 cc (as compared to approximately 350 mL during a donation). Theoretically, if too much blood is lost, this could lead to low blood pressure and cardiovascular stress or dizziness.

Withdrawal of CPAP: During abstinence from CPAP over 3 days, subjects may experience relatively unrefreshing sleep. During the night, they may experience arousals from sleep, morning headache. During the daytime, they may experience subjective and/or objective daytime sleepiness. The risk of sleepiness contributing to an accident such as work-related injury or motor vehicle collision is also increased. Chronically, OSA is associated with increased risks of hypertension, diabetes, stroke, and ischemic heart disease. In a recent study on the effects of 2-weeks of CPAP withdrawal, there were modest and gradual increases in daytime blood pressure, heart rate, and triglycerides⁷. Risks of stopping CPAP for 2 weeks is therefore a low-risk, high yield research method. In this study, withholding CPAP for a few days is associated with even fewer risks.

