Nasal dilator strips: These are non-latex, adhesive tape applied to the nose designed to mitigate snoring and nasal congestion. There may be discomfort using NDS, and they are inferior to CPAP for treating OSA.

DEXA scan: DEXA scans are considered safe and deliver minimal radiation.

Oral glucose tolerance test: There are no significant risks to this standard clinical test other than the associated phlebotomy.

EndoPAT: There are no significant risks to this test other than arm discomfort during the procedure.

Confidentiality of genetic material: There is the risk that genetic data is revealed outside the study. Information can also lead to unwanted psychological or financial consequences if it were released to a third party.

b. Steps taken to minimize the risks.

Veni-Puncture: Discomfort, bruise formation, and infection will be minimized by use of sterile supplies and aseptic technique by trained personnel.

Phlebotomy: The volume of each blood draw is minimized to balance safety with the need to obtain a useful amount of plasma after centrifugation. The risk of inducing hemodynamic or cardiovascular stress is minimized by excluding those with significant baseline anemia (hemoglobin <10 mg/dl). Those found to have anemia will be informed of the results and advised to seek medical evaluation as appropriate.

Withdrawal of CPAP. Subjects will be advised to arrange transportation home so that they do not need to drive. They will be advised to increase their total sleep time, if necessary, during CPAP abstinence to minimize sleep deprivation off CPAP. On the day of the non-CPAP sleep study, if they plan to drive home themselves, they will be provided with an additional 3-4 hours of time in the lab to sleep before discharge. Participants with high-risk occupations requiring vigilance, such as commercial drivers and pilots, will be excluded. Participants who have ever been in a near-miss or motor vehicle accident due to sleepiness will be excluded. When communicating with patients about their off-CPAP visits, patients will be asked in the 1-2 days before their visit if they have experienced any near-miss events or motor vehicle accidents. If they have, then they will be excluded from the study, advised to resume CPAP immediately, and to avoid driving or other high risk activities until they have used CPAP for 3 nights.

DEXA scan: DEXA uses a beam of very low radiation, delivering <10% radiation as during a clinical chest X-ray.

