NDS: This is only being used for a few nights as a CPAP placebo.

Oral glucose tolerance test: The phlebotomy associated with this procedure will be performed by experienced personnel.

EndoPAT: This procedure will be performed only by trained study team members or Core physiology lab members. Any complications will be evaluated by a physician. In the case of an adverse event, the subjects will be referred to the appropriate clinical specialist, either outpatient or inpatient for care. Adverse events related to the study procedures will be reported to the IRB.

Confidentiality of genetic material: Blood is de-identified using the study IDs. When DNA is purified, a second number will be assigned to the DNA material. We will maintain a separate “key” linking this DNA sample to the study ID. This “key” will be stored on an encrypted server, and access to this server will be limited to only certain members of the study team. Participants may opt out from the genetic analysis.

c. Plan for reporting unanticipated problems or study deviations.

The plan for collection, description, monitoring and analysis of adverse events is presented in accordance with guidelines for adverse event reporting to the IRB.

We will use the following definitions and grading scales for monitoring purposes:

Definition of adverse event (AE): any unfavorable and unintended sign (including an abnormal laboratory finding), symptom or disease temporarily associated with the use of a medical treatment or procedure regardless of whether it is considered related to the medical treatment or procedure

Definition of serious adverse event (SAE): any event that is fatal or life-threatening, that is permanently disabling, requires or extends hospitalization of the subject, represents a significant overdose or breach of protocol, suggests that a drug, device, or procedure used in a research protocol has produced a congenital anomaly or cancer, or in the opinion of the investigator, represents other significant hazards or potentially serious harm to the research subject or others

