Adverse events will be graded as (a) mild (adverse event of little clinical significance), (b) moderate (adverse event between mild and severe – causing some limitation of usual activities), or (c) severe (an event that results in death, is life-threatening, requires or prolongs hospitalization, causes persistent or significant disability/incapacity, represents a significant overdose or breach of protocol, results in congenital anomalies/birth defects or produces cancer, or in the

opinion of the investigator, represents other significant hazards or potentially serious harm to the research subject or others), and their attribution will be classified as (a) not related (clearly not related), (b) possible (may be related), (c) probable (likely related), (d) definite (clearly related) or (e) unable to assess.

Study participants will be monitored throughout the study for adverse events, both anticipated and unexpected. The Principal Investigator will serve as the monitor. Adverse events will be reviewed by the Principal Investigator, managed according to standard clinical practice, and classified for severity and attribution. Serious adverse events or unexpected adverse events will be recorded on the appropriate IRB form and reported to the IRB and RSA as required. All adverse events will be tracked to resolution.

The principal investigator will provide an interim report of all adverse events to the IRB at the time of continuing review. In addition, the Principal Investigator will provide the RSA a tabulation of the number of subjects enrolled, number of specific adverse events and a summary of the study at regular intervals. The RSA in collaboration will monitor the frequency of adverse events and serious adverse events.

d. Legal risks such as the risks that would be associated with breach of confidentiality.

Breach of confidentiality would result in unauthorized individuals having access to information about the participant's medical history. To prevent unauthorized access, (1) all files related to study subjects will be locked in file cabinets; (2) digital files will be restricted to study investigators and associated staff, on a need-to-know basis. (3) Subject data will be stored with unique identifiers and will be password protected. Encryption algorithms that can only be reversed with password access will be implemented. All computers will require log on passwords.

e. Financial risks to the participants.

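### Does the early stopping rule, which ends in study discontinuation after any serious adverse event, leave the statistical plan unsound?

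*Combined protocol and SAP*

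**What the plan says.** The Early stopping rule, placed after the sample size under Study Statistics, is one short paragraph. It opens with the individual subject's right to decline. It continues "Indications for stopping are the development of severe adverse events", then "The DSMB and IRB will be informed of any adverse events", and ends "Any serious adverse events will result in study discontinuation". It gives no condition on causality and does not name the unit that stops.

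Other sections bear on it:

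- Section 4f, on participant removal, lists only inability to tolerate being off CPAP.
- Section 7b covers participants who report a near-miss or motor vehicle accident when asked before an off-CPAP visit: "If they have, then they will be excluded from the study, advised to resume CPAP immediately".
- Section 7c defines an adverse event "regardless of whether it is considered related to the medical treatment or procedure". Its definition of a serious event includes one that "requires or extends hospitalization of the subject, represents a significant overdose or breach of protocol".
- Section 7c defines the top grade as "severe (an event that results in death, is life-threatening, requires or prolongs hospitalization", followed by most of the other criteria for a serious event. For every event, "their attribution will be classified as (a) not related (clearly not related), (b) possible (may be related" and so on.
- Section 7c names the Principal Investigator as monitor. Serious events are reported to the IRB and the RSA, and the RSA monitors how often they occur. It does not mention a DSMB.

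**The concern.** A sentence under a heading about early stopping, with a mandatory verb and a threshold of one event, reads naturally as a rule for the whole trial. On that reading an unrelated admission, or a significant protocol breach, would end the study. Monitoring the frequency of serious events would then have little purpose, since there could be only one before the stop, and the attribution classes would have no bearing on it.

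On the other reading, where only the affected participant leaves, the paragraph contains no rule for the trial at all.

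Two further points add to the impression of a defect. The paragraph uses *severe* and *serious* as if they were different triggers, although section 7c defines them almost identically. It also informs a DSMB, while section 7c works through the Principal Investigator and the RSA. At stake would be an unplanned early end and loss of power for the comparison on which the study is sized.

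**Working it through.** **The plan's own figure.** Inputs from the Sample Size paragraph: mean change 0.047 in men and 0.021 in women, SD 0.04 mmol/l in both, 80% power, alpha 0.05 (taken as two-sided), 15% loss.

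- d = (0.047 − 0.021)/0.04 = 0.65.
- A two-sample t-test needs 38.14 per group, so 39 per sex and 78 in all. Power at 39 per sex is 0.809.
- 78/0.85 = 91.8, rounded up to 92.

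The stated 78 and 92 reproduce. The stopping rule enters none of these steps.

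**The two readings against the rest of the text.**

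| Text | Trial stops | Participant stops |
|---|---|---|
| Opening sentence of the paragraph (a subject may decline) | different level | same level |
| Heading of the paragraph | fits | fits poorly |
| 4f, removal criteria | silent on serious events | silent on serious events |
| 7b, near-miss or accident | no conflict: not a serious event as such | fits |
| 7c, definition regardless of relatedness | no conflict with a rule covering any event | no conflict |
| 7c, attribution classes | no conflict: they apply to all adverse events | no conflict |
| 7c, RSA monitors frequency of serious events | awkward | fits |

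Only the last row sets one section against another, and only on the trial-level reading. The section 7b triggers would overlap with the rule only if an accident also met the definition of a serious event, for example through hospital admission.

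**Size on the participant-level reading.** Each event removes at most one subject. The enrolment target leaves 92 − 78 = 14 subjects for losses, although the plan intends that margin for technical failures. If the margin were already used up, one further loss (39 and 38 per sex) would give power of 0.804 and two (39 and 37) 0.798.

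**Size on the trial-level reading.** The documents give no rate, so only ranges are possible.

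- Per-subject risk at which at least one event among 92 becomes as likely as not: 1 − 0.5^(1/92) = 0.0075, or 0.75%.
- For an assumed per-subject risk p, the chance of at least one event is 1 − (1 − p)^92: 9% at p = 0.1%, 37% at 0.5%, 60% at 1%, 84% at 2%.
- For an assumed rate of 5 to 10% per person-year, the chance is 1 − exp(−92 × years × rate): 4 to 7% over 3 days (the CPAP-withdrawal nights) and 68 to 90% over 3 months (the longest permitted gap between visits).

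A result that runs from 4% to 90% according to the assumed rate and window is not an estimate.

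**Power if the trial stopped at half the evaluable sample (39 subjects; the halfway point is arbitrary).**

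- Sex comparison: 19.5 per sex, d = 0.65, power 0.507.
- CPAP against OSA night (the Aim 1 primary outcome, within subject): with equal numbers of men and women the mean change is (0.047 + 0.021)/2 = 0.034. The SD across both sexes is √(0.04² + 0.013²) = 0.042, where 0.013 is half the difference between the sexes. The standardised change is 0.034/0.0421 = 0.81. A paired t-test then has power 0.998 at 39 subjects and 0.93 at 20. This reads ± as SD and assumes that the preliminary change carries over to the two-night design.

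**Validity.** The trigger is a safety event. No FFA result is tested to decide on stopping, so on neither reading is there an interim test that would need a correction to alpha. An early end would cost precision, not error control.

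**The case for a change.** The strongest argument for acting is that the sentence is mandatory, has a threshold of one, sits under a stopping heading and is explained nowhere else. A study team faced with an unrelated admission could not tell from the text whether to halt enrolment, and no section says who decides. The comparison exposed to an early halt is the one the study is sized on, and reconciling the text would cost only a wording amendment.

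Much of this stands. The unit is not stated. The overlap of *severe* and *serious* is real, and so is the mention of a DSMB in one place only. These are points of loose drafting, however. Because the two terms are defined almost alike, the two sentences can be read as saying the same thing twice. Informing a DSMB does not exclude monitoring by the Principal Investigator and tabulation for the RSA.

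The argument fails at the step from unclear wording to a flaw in the plan. It asks the sponsor to write down a unit, a trigger term and a deciding body, and none of these alters a number, a model or an analysis population. The wider claim, that sections 7b and 7c as a whole contradict the rule, does not hold: of the texts cited, only the frequency monitoring is awkward, and then on one reading.

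**Conclusion.** No change to the statistical plan follows. The Early stopping rule is ambiguous about what is discontinued. Read at trial level, it sits awkwardly with the frequency monitoring in section 7c. The terms and the oversight bodies in these sections should be reconciled by the sponsor and IRB as a matter of safety wording, and this review takes no view on which rule is right.

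Statistically, this is missing detail that a study team can settle with its IRB when an event occurs. Under a participant-level reading, which the other safety sections largely fit, the cost is one subject per event and the conclusions stay sound. Under a trial-level reading the cost depends on an event rate that the documents do not give and on when the stop falls: about 51% power for the sex comparison at an arbitrary halfway stop, little loss near completion, and ample power for the within-subject CPAP comparison in either case, if the preliminary change carries over. The sample size of 78 evaluable and 92 enrolled reproduces and is unaffected.

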Sequence and Timing of visits: Each subject will undergo up 2 visits to the lab. One sleep study will be conducted while wearing CPAP for the entire night. The second sleep study will be conducted using nasal dilator strips (NDS) as a placebo, instead of wearing CPAP, the entire night. NDS have been used in other studies as a CPAP placebo and have no impact on OSA severity [6]. The studies will be performed in random order, occurring >1 week apart and no longer than 3 months apart. To maximize chances of eliciting OSA during the non-CPAP study night, patients will be asked to refrain from CPAP use, for two nights preceding their non-CPAP study night. They will be provided with ClearPassage® NDS to use at home during CPAP withdrawal nights. This will ensure CPAP “washout” since therapeutic carryover effects of CPAP have been observed in some studies[7]. Patients who were previously enrolled in the single-night study (within-night CPAP withdrawal) will be invited to return for these additional sleep studies.

Study eligibility: To be enrolled in the study, participants will need to undergo a screening questionnaire and meet inclusion/exclusion criteria. They will need to provide written consent for participation. To avoid issues of CPAP intolerance, participants must also be accustomed to using CPAP, and report that they are capable of sleeping with CPAP on.

As of March 16, 2020 (or approval of this eFormA update), and in order to mitigate risks related to COVID-19 exposure to participants and study team, phone screening procedures will be completed from the study team members' home using a connecting service, such as Google Voice or Skype Voice-to-IP to protect study team members' personal contact information while allowing them to continue job functions from a safe location. Participants will be notified of the change in procedure.

Consent: In order to minimize the need for research-only in-person visits, telemedicine visits may be substituted for in person clinical trial visits or portions of clinical trial visits where determined to be appropriate and where determined by the investigator not to increase the participants' risks. Prior to initiating telemedicine for study visits

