PSG setup. On each study night from 22:40 until 06:40, a PSG will be performed. The sleep study will include electroencephalography, electrooculography, oxygenation, respiratory effort, CPAP airflow, and transcutaneous CO₂ monitoring. Respiratory effort will be measured by thoraco-abdominal movement assessed by mercury strain gauges. Surface electrodes will be placed at C₃A₂ and C₃O₁, a submental electrode, and left and right electro-oculogram will be used to stage sleep. Electrocardiograph (EKG) tracings will be recorded from three chest electrodes. Continuous measurement of oxygen saturation will be recorded using an ear oximeter (model No 472-1A, Hewlett Packard, Waltham, Mass). Transcutaneous CO₂ will be monitored using a Radiometer TCM-4 device. Signals from the electroencephalograph, EKG, electromyogram, electrooculogram, respiratory strain gauge, ear oximeter and thermistors will be recorded on a computer with RemLogic software.

During the CPAP night, patients will sleep using CPAP set to their prescribed home CPAP settings. Airflow will be recorded with a pneumotachograph in the CPAP circuit. CPAP pressure will be titrated if necessary to prevent

obstructive hypopneas and apneas. During NDS nights, ClearPassage® strips will be applied at bedtime. Flow will be measured using a nasal cannula and oral thermistor.

[figure not shown]
Blood work and urine collection

All samples will be obtained via the indwelling IV, without awakening the subject. Blood samples will be drawn at 30 to 60 minute intervals beginning at 5:30 PM and continuing until the next morning at 6:30 AM as shown in the figure below. At 10:30 PM, when the sleep study starts, blood is sampled at 30 minute intervals in order to capture dynamic changes in FFA metabolism during sleep. Each blood sample will be 4 cc in volume and placed into lavender top tubes (EDTA) for centrifugation to obtain plasma. Cells are removed from plasma by centrifugation for 10 minutes at 1500 x using a refrigerated centrifuge. If necessary, based on nursing schedules, the timing of sampling and sleep procedures can be shifted up to 1 hour later or earlier.

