Following centrifugation, plasma will be transferred to cryovials for storage. The final morning sample at time of awakening (6:30 AM) will be 12 cc (3 tubes) since we plan additional assays with this sample (lipid panel, inflammatory markers) and 4 cc will be retained as whole blood for future potential analysis. In patients that have signed the optional consent for isolation of genetic material, we will collect an additional 16 cc (4 tubes) at 6:30 AM since this volume is required for isolation of peripheral mononuclear cells. In total, the blood collected will be approximately 174 cc. For patients that consent to isolation of genetic material, the total will be 190 cc. This quantity is much less than during a blood donation. Samples will be frozen at -80°C for research pertaining to metabolic effects of OSA, with the consent of participants. A morning urine sample will be collected for measurement of catecholamines.

Morning procedures:

The PSG montage will be disconnected. One IV is removed, leaving the other IV in place for use during later glucose tolerance test. Then peripheral artery tonometry, DEXA scanning, and OGTT will be performed as follows:

Peripheral arterial tonometry (EndoPAT). The subject will be in the supine position. A blood pressure cuff is placed on the non-dominant arm while the contralateral arm is used for control comparisons. Baseline measurements will be taken for 5 minutes, during 5-min occlusion of the brachial artery by inflation of the automated cuff 50 mmHg above systolic blood pressure, and for 5 minutes upon release of the cuff. Endothelium-mediated vasodilation is assessed using a finger pulse wave amplifier. The reactive hyperemia index (RHI) and the augmentation index (AI) will be derived by software and used as metrics of endothelial function and arterial stiffness respectively.

Oral glucose tolerance test (OGTT). From the indwelling antecubital IV, baseline insulin (gold top tube, 4 cc) and glucose (grey top tube, 4 cc) will be obtained. The patient will be given a 75 g glucose solution to drink within 5

minutes. Blood samples of insulin and glucose are then collected at 30, 60, 90, and 120 minutes after drinking the glucose solution. They will be asked, if possible, to remain awake during the OGTT.

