Dual-energy X-ray absorptiometry (DEXA). After the baseline glucose level for the OGTT has been drawn and the patient has consumed the glucose solution, they will undergo a DEXA scan. The DEXA scan will be used to estimate fat mass, which will be one of the variables analyzed as a predictor of FFA elevation.

Subjects may eat breakfast after the OGTT testing is completed

To minimize the impact of sleep loss on driving safety, subjects are asked to either (1) arrange for an alternate means of transportation home (this is mentioned on the consent or to (2) sleep as needed for up to 4 additional hours before discharge.

Repeat sleep testing:

Repeat sleep tests may be requested from the subject under the following circumstances:

- (1) A technical problem with data acquisition including PSG lead failure/artifacts, incomplete blood collection from IV insertion or maintenance problems.
- (2) Poor sleep efficiency <50% of time in bed

If the initial sleep study meets these criteria and a repeat test is deemed necessary by the PI, then the repeat testing will be scheduled at least 1 week following the initial study.

Scoring. Sleep will be scored according to Rechtschaffen and Kales criteria. Respiratory events will be scored according to AASM criteria. Apneas will be considered present when there is no air flow for >10 seconds. Obstructive apneas will be considered present when apneas are associated with positive strain gauge deflections indicating thoracic movement. Apneas will be considered central in origin when cessation of air flow is not accompanied by thoracic movement as measured by the strain gauge. Mixed apneas will be defined by episodes of no air movement resulting from central apnea followed by obstruction. Hypopneas will be scored for reductions in airflow of 30% lasting >10 seconds accompanied by either an arousal or fall in oxyhemoglobin saturation of 3% or greater.

Data Analysis and Anticipated Outcomes:

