The primary outcomes is nocturnal plasma FFA levels. The main independent variable is OSA versus CPAP exposure during sleep. Since FFA are measured multiple times per subject per night, we will perform mixed linear model analysis using condition as a fixed factor and subject ID as a random factor. Sleep physiology that is measured on a continuous basis will be condensed into 30 minute bins to create a parallel data structure with metabolic parameters. As a secondary analysis, we will also examine whether there are patient-specific (“static”) determinants of FFA level during sleep such as age, sex, or body mass index and whether these variables interact with sleep (“dynamic”) variables such as OSA severity. We hypothesize that OSA exposure increases FFA, compared to CPAP. We will then examine whether sleep physiology (e.g. AHI, arousals, heart rate) is dynamically associated with FFA, and whether urine catecholamine levels are associated with increases in FFA. For variables measured once (RHI, morning lipid profile) or averaged (e.g. nocturnal FFA level) we will perform one-way ANOVA for comparisons. We will also compare sleep physiology between the 3 nights, examining variables such as apnea hypopnea index, metrics of hypoxia, and sleep architecture/duration. Data analysis will be performed with a biostatistician and described under the “Study Statistics” section.

b. Study duration and number of study visits required of research participants.

Each study subject will make two overnight visits to the sleep lab. Subjects will be screened with an initial telephone interview. During this screening, only information necessary to assess eligibility for the study will be collected, or information voluntarily provided by the patient to initiate or maintain correspondence. Subjects without any of the self-reported exclusionary criteria will be scheduled for a face-to-face visit for further screening. At this visit, eligibility for

participation in the study protocols will be confirmed. Urine screening for pregnancy in women of child-bearing age will also be performed.

c. Blinding, including justification for blinding or not blinding the trial, if applicable.

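### The 174 cc given as the blood collected in total can only be one visit's volume; the two-visit total is missing, and on that basis the favourable comparison with a donation does not hold

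*Combined protocol and SAP*

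**What the plan says.** Two places give the volume. Section 4a, Blood work and urine collection, states: "In total, the blood collected will be approximately 174 cc". It continues: "For patients that consent to isolation of genetic material, the total will be 190 cc". It then concludes: "This quantity is much less than during a blood donation". Section 7a, Phlebotomy, repeats the figure and adds a comparator: "In total, the blood collected will be approximately 174 cc (as compared to approximately 350 mL during a donation". Neither place says whether the volume is per visit or for the whole study.

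The number of visits is fixed elsewhere. Section 4b says: "Each study subject will make two overnight visits to the sleep lab". Section 4a, Sequence and Timing of visits, gives the spacing: "The studies will be performed in random order, occurring >1 week apart and no longer than 3 months apart". Section 9a pays for a glucose tolerance test after each of the two visits. Section 4a, Repeat sleep testing, allows further nights: "Repeat sleep tests may be requested from the subject under the following circumstances". The listed circumstances are technical failure, including incomplete blood collection, and poor sleep efficiency.

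**The concern.** A figure described as a total, placed in the list of the study's medical risks, will be read as what a participant gives over the study. If it covers only one of two planned visits, whoever weighs the phlebotomy risk sees roughly half of the planned exposure, and sees it set against a 350 mL donation that the two-visit volume may equal. No endpoint, analysis or sample size depends on this. What is at stake is whether a stated safety figure is correct.

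**Working it through.** **Inputs, all from section 4a unless noted**
- Sampling window: "Blood samples will be drawn at 30 to 60 minute intervals beginning at 5:30 PM and continuing until the next morning at 6:30 AM", and half-hourly from 10:30 PM.
- Volume: 4 cc per sample; 12 cc for the final 6:30 AM draw. A further 4 cc is kept as whole blood, and the text does not settle whether this lies inside the 12 cc.
- Genetic sample: 16 cc at 6:30 AM.
- Oral glucose tolerance test (OGTT): baseline 4 + 4 = 8 cc, then four more time points. Assumption: the later tubes match baseline, so 5 × 8 = 40 cc.
- Visits: 2 (section 4b). Donation: about 350 mL (section 7a).

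**Step 1. Can 174 cc cover both visits?** From 10:30 PM to 6:30 AM there are 17 half-hourly samples: 16 of 4 cc and a last one of 12 cc. From 5:30 PM until then there are at least 5 samples (hourly) and at most 10 (half-hourly).
- Smallest overnight volume: 5 × 4 + 16 × 4 + 12 = 96 cc per visit.
- Two visits: 2 × 96 = 192 cc, already above 174 cc with no OGTT blood counted.

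So 174 cc cannot be the two-visit total.

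**Step 2. What does the genetic step show?** 190 − 174 = 16 cc, exactly one 6:30 AM genetic draw. This also fits one-visit accounting.

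**Step 3. Is 174 cc reproduced as one visit?** Visit volume = evening samples × 4 + 16 × 4 + final draw + 40.
- Lowest: 20 + 64 + 12 + 40 = 136 cc.
- Highest: 40 + 64 + 20 + 40 = 164 cc, taking half-hourly evening draws and a final draw of 4 routine + 12 + 4 whole blood.

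The highest variant is 10 cc (about 6%) short of 174 cc. The text refers to a sampling figure that is not shown in this copy, and that figure may explain the gap.

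**Step 4. Two visits, against 350 mL**

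| Basis | One visit, cc | Two visits, cc | Two visits / 350 |
|---|---|---|---|
| Stated, no genetic sample | 174 | 348 | 99% |
| Stated, genetic sample at one visit | n/a | 348 + 16 = 364 | 104% |
| Stated, genetic sample at both | 190 | 380 | 109% |
| Itemised, no genetic sample | 136-164 | 272-328 | 78-94% |
| Itemised, genetic sample at both | 152-180 | 304-360 | 87-103% |

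For one visit on the stated figures, 174/350 = 50% and 190/350 = 54%. Even the lowest two-visit tally is 272/174 = 1.56 times the stated total.

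**The case against.** The strongest reply is that the figure was always meant per visit. Section 4a describes one night and morning, its total closes that description, and the 16 cc step fits. On that reading 50-54% of a donation is indeed much less. The harms named in section 7a (low blood pressure, cardiovascular stress, dizziness) can be read as effects of one session's loss, and the visits are more than a week apart. This stands, and it rules out saying that the donation comparison is simply false. It does not remove the point: the text says total, gives no per-visit label, and states no cumulative volume anywhere.

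A reader might also infer more than the documents support:
- **That two visits take 348 or 380 cc as a matter of fact.** Both figures double a 174 cc that the listed draws do not reproduce. Without genetic samples, the itemised two-visit volume stays below 350 mL. The 380 cc also needs genetic samples at both visits. The exploratory aim on gene expression after CPAP withdrawal makes this plausible, but it is not stated.
- **That exposure could be three times the stated figure.** This requires a full extra night. Repeats are conditional and at the investigator's discretion, one trigger is that blood collection was incomplete, and the text does not say that a repeat includes the OGTT or the genetic draw.
- **That the hemoglobin exclusion rests on 174 cc.** Sections 4a and 7b tie it to pre-existing anemia, and nothing derives it from this volume.
- **That participants were told the wrong volume.** The consent text is not available to check.

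**Conclusion.** The point holds in a limited form. As a study total, 174 cc (190 cc with genetic samples) is wrong. That conclusion needs only the overnight schedule and the two visits, and does not depend on the OGTT assumption or the missing figure. As a per-visit figure it is plausible but not reproduced.

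The corrected two-visit volume is a range: 272-328 cc from the itemised draws or 348 cc from the stated figure, without genetic samples; 304-360 cc or 380 cc with them at both visits. Across these bases it is 78% to 109% of the protocol's own donation figure. The claim of being well below a donation therefore holds for one visit and fails for the study. This is a wrong safety figure that should be corrected. It does not show that the sampling is unsafe.

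**What to change.** In section 4a (Blood work and urine collection) and section 7a (Phlebotomy):
- label 174 and 190 cc as per visit;
- reconcile them with the itemised draws, stating the number of evening samples, whether the 4 cc of whole blood is inside the 12 cc, and the tube volumes at the later OGTT time points;
- add the cumulative two-visit volume, and say whether genetic samples are taken at one visit or both;
- note that a repeat night would add up to about one more visit's volume;
- state the donation comparison as per visit, or delete it.

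The reconciliation should come first, so that 348 or 380 cc is not written in on the strength of an unverified 174. The sponsor and the IRB should then check the phlebotomy risk text against the corrected figures. The cost is wording only, with a less favourable risk statement. No change to sampling or to any clinical limit is proposed.
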